## **13. statistic analysis**

### **13.1 Sample size determination**

In this study, 1:1 parallel control was used to estimate the sample size according to the group design of two sample rates comparison sample content estimation formula:

$$n = \frac{2 \times (U_\alpha + U_\beta)^2 \times P \times (1-P)}{(P_1 - P_2)^2} \quad P = \frac{(P_1 * n_1 + P_2 * n_2)}{(n_1 + n_2)}$$

Where,  $U_\alpha$  is the first type of error probability  $U$  value,  $U_\beta$  is the second type of error probability, when bilateral  $\alpha=0.05$ , unilateral  $\beta=0.1$ ,  $U_\alpha=1.96$ ,  $U_\beta=1.28$ ,  $P_1$  is the effective rate of the treatment group,  $P_2$  is the effective rate of the control group, and  $P$  is the rate of the two combinations. According to previous research literature,  $P_1$  and  $P_2$  are estimated to be 79.4% and 54.8%, resulting in  $n \approx 76$ , and the minimum sample size of each group is about 76 cases. As shedding cases were not excluded during the study, the shedding rate was 15%. For the successful completion of the experiment, 87 cases were assigned to each group based on various factors, and 174 cases were required to be included in the two groups.

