| statistic analysis  | 
Analysis set
 
Statistical analysis was carried out using full analysis set, coincidence scheme set and security analysis set.
 
Full analysis set (FAS) : Included all randomised participants who had received at least one study intervention and had a measurable baseline stroke.
 
Per Protocol Set (PPS) : In the FAS population, participants with at least one post-intervention awareness scale assessment, good adherence, and no significant violations or deviations from the trial protocol.
 
Safety Set (SS) : defined as subjects who received at least one intervention and were subsequently evaluated for safety.
 
Sample size determination: The sample size is estimated according to
 |

|                           |  |
|---------------------------|--|
|                           | 
the group design of two sample rates compared sample size estimation formula
 $n = \frac{2 \times (U_\alpha + U_\beta)^2 \times P \times (1-P)}{(P_1 - P_2)^2}$ $P = \frac{(P_1 * n_1 + P_2 * n_2)}{(n_1 + n_2)}$ 
Where, <math>U_\alpha</math> is the first type of error probability <math>U</math> value, <math>U_\beta</math> is the second type of error probability, when bilateral <math>\alpha=0.05</math>, unilateral <math>\beta=0.1</math>, <math>U_\alpha=1.96</math>, <math>U_\beta=1.28</math>, <math>P_1</math> is the effective rate of the treatment group, <math>P_2</math> is the effective rate of the control group, and <math>P</math> is the rate of the two combinations. According to previous research literature [1], <math>P_1</math> and <math>P_2</math> are estimated to be 79.4% and 54.8%, resulting in <math>n \approx 76</math>, and the minimum sample size of each group is about 76 cases. As shedding cases were not excluded during the study, the shedding rate was 15%. For the successful completion of the experiment, 87 cases were assigned to each group based on various factors, and 174 cases were required to be included in the two groups.
 
Statistical analysis: All data in the experiment were tested and analyzed for normality, and SPSS 25.0 statistical software was used for analysis and processing.
 |
| follow-up          | Telephone and video follow-up  |

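### The stated minimum of about 76 per group, 15% drop-out and 87 enrolled per group do not agree with one another, though the effect on power is minor

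*Combined protocol and SAP*

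**What the plan says.** The sample-size paragraph appears twice, in the Summary of research scheme (statistic analysis row) and in Section 13.1, with the same figures. It compares two proportions with 1:1 allocation, two-sided alpha 0.05 and beta 0.1 (U values 1.96 and 1.28). The effective rates for treatment and control "are estimated to be 79.4% and 54.8" per cent. It concludes that "the minimum sample size of each group is about 76 cases". It then says that "the shedding rate was 15%. For the successful completion of the experiment, 87 cases were assigned to each group", attributing the 87 to various factors, for a total of 174. Neither place gives the formula that leads from 76 to 87.

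Two other places bear on the point. The Expected progress row of the Summary and Section 14.4 set aside 2025 for adding cases to make up those lost. Section 13.2 keeps in the full analysis set anyone treated at least once and assessed for effectiveness at least once.

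**The concern.** A drop-out allowance should let the enrolled number, after the stated loss, still meet the stated minimum. Here it does not: 85% of 87 is below 76. The likely cause is that the allowance was applied by multiplying by 1.15 when the loss should be divided out (by 0.85). In addition, the base figure of 76.59 was rounded down where a minimum is normally rounded up. Both steps make the target smaller.

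What is at stake is whether the design figure is internally correct. A reader of Section 13.1 is told that 174 patients allow for 15% loss at 90% power, and by the plan's own formula they do not quite do so.

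**Working it through.** **Inputs (Section 13.1, repeated in the Summary).** P1 = 0.794, P2 = 0.548, difference 0.246; pooled P = (0.794 + 0.548)/2 = 0.671; U values 1.96 and 1.28; loss 15%; enrolled 87 per group.

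**1. The plan's base figure.** n = 2 x (1.96 + 1.28)^2 x 0.671 x 0.329 / 0.246^2 = 76.59 per group. The stated figure of about 76 is this rounded down; rounded up it is 77.

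**2. From 76 to 87.**
- Multiplying: 76 x 1.15 = 87.4, which gives 87 if rounded down.
- Dividing: 76/0.85 = 89.4, so 90; 77/0.85 = 90.6, so 91.

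Only the multiplication matches the stated 87. The next two steps do not depend on how 87 was reached.

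**3. What 87 delivers without replacement.**
- At 15% loss: 87 x 0.85 = 73.95, about 74 completers per group.
- Largest loss that leaves 76: 1 - 76/87 = 12.6%.
- Largest loss that leaves 77: 1 - 77/87 = 11.5%.

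**4. Power.** Inverting the plan's formula, power = Phi(0.246 / sqrt(2 x 0.671 x 0.329 / n) - 1.96). The second column uses the pooled variance under the null and separate variances under the alternative. The third is exact enumeration of the uncorrected chi-square test.

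| n per group | Plan's formula | Pooled null, separate alternative | Exact chi-square |
|---|---|---|---|
| 74 | 89.0% | 89.8% | 90.0% |
| 76 | 89.75% | 90.55% | 90.6% |
| 77 | 90.1% | 90.9% | 91.1% |

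By the plan's formula, rounding 76.59 down to 76 costs about 0.25 points against the 90% target, and going from 76 to 74 costs a further 0.8 points or so.

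**The case against.** The strongest objection is that a completer is not the same as an analysed patient, and that lost patients are to be replaced.

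- **Replacement.** The Summary and Section 14.4 plan to add cases in 2025 for those lost, so 74 need not be the final count. This stands: the shortfall holds only if no one is replaced. It does not rescue the figure of 174, however. If the added cases fall within 174, they restore nothing. If they come on top, reaching 76 or 77 completers at 15% loss takes enrolment to 90 or 91 per group (180 or 182), above the stated total. The documents give no replacement rule, cap or final number.
- **Analysis set.** GCS is scored weekly, so a patient who leaves after week 1 stays in the full analysis set of Section 13.2. This also stands, and the 74 should be read as completers. But the responder rate in Section 8.1.1 needs a score after treatment, and no rule is given for a patient who leaves before week 4.
- **Inference.** The plan cites various factors for the 87, so the 1.15 multiplier is not documented. This is conceded; the mismatch between 76, 15% and 87 remains either way.
- **Materiality.** The result is far more sensitive to the assumed rates: with P1 at 78.4%, the same formula gives 2 x 10.4976 x 0.666 x 0.334 / 0.236^2 = about 84 per group. Section 4 states 72 patients in total, and Section 13.3 analyses scores by analysis of variance while the sample size rests on rates. Both are separate points and weigh more than this one.

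A reader might infer that the trial loses its 90% power, or that it will fail to reach its own minimum. The documents support neither. At 74 per group the shortfall is one point by the plan's formula and nil by exact chi-square. A Fisher test would give 86.2%, but none is planned for efficacy. An unmet minimum would require 15% loss with no effective replacement, and the plan provides for replacement.

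**Conclusion.** The point holds as a small arithmetic inconsistency in a stated design figure. A minimum of about 76, a 15% loss and 87 enrolled per group cannot all be right: 87 is 3 to 4 per group (6 to 8 in total) below what a 15% allowance without replacement implies. The loss of power is at most about one percentage point. This rests on the plan's own rates and formula, on counting completers, and on no replacement. Rounding to about 76 would not merit comment by itself. The reason to act is that the figures disagree and the correction is cheap.

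**What to change.** Restate the paragraph in both the Summary and Section 13.1 along these lines: the formula gives 76.59, rounded up to 77 per group; 87 enrolled per group covers about 11.5% loss at 90% power, or leaves about 74 completers (about 89% power by the stated formula) at 15% loss if no one is replaced.

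Add one sentence saying whether the cases to be added in 2025 come on top of 174 or within it, and make the Expected progress row and Section 14.4 agree. Note that a 15% allowance without replacement corresponds to 90 to 91 per group (180 to 182 in total).

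The cost is a few sentences and a slightly less favourable stated figure. No extra patients are needed if the figure is simply restated; keeping 15% loss and 90% power together, without replacement and from 77, would need 91 per group, 8 more patients than 174.

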### **13.2 Analysis set definition and selection**

A Full Analysis Set (FAS) is a set of participants who have received the investigational drug at least once since enrollment and have been evaluated for effectiveness at least once.

Safety Set (SS) : The set of all subjects who received the investigational drug at least once after enrollment and were evaluated for safety at least once.

Per Protocol Set (PPS) : The set of cases in which all patients in the full analysis completed protocol treatment and did not seriously violate the protocol.

### **13.3 Statistical method**

The analysis included case distribution, demographic data, baseline analysis and therapeutic effect analysis. Baseline data included sex, age, stroke type, stroke duration, underlying medical history (diabetes, hypertension, heart disease, chronic obstructive pulmonary disease), and history of smoking and alcohol use. Baseline data were tested by chi-square test. The end point data was the score of the State of Consciousness scale, and the measurement data was expressed as mean SD. Univariate analysis of variance was used to compare the difference between groups at the same time point, the difference at different time points in the group, and the difference before and after between the two groups.  $P < 0.05$  was considered statistically significant, and multiple comparisons were performed by Dunnett-t test.

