## Summary of research scheme

|                            |  |
|----------------------------|--|
| scheme name         | Study on the effect of Tongyuan acupuncture on consciousness disorder after stroke   |
| applicant           | Nanfang Hospital, Southern Medical University  |
| major investigators |  |
| research center     | Department of Rehabilitation, Nanfang Hospital, Southern Medical University  |
| research object     | Stroke patients with conscious disturbance   |
| purpose of research | Objective: To investigate whether Tongyuan acupuncture can improve the consciousness disorder after stroke
Secondary objective: To investigate the possible mechanism of action   |
| Research grouping   | Trial group: Tong Yuan acupuncture, once a day, 5 days a week for 4 consecutive weeks.Twenty days in total.
Control group: pseudoacupoint method, once a day, 5 days a week for 4 consecutive weeks.Twenty days in total.   |
| study design        | This study was a randomized, placebo-controlled, single-blind study. Patients with post-stroke consciousness disorder hospitalized in the rehabilitation Department of Southern Hospital were randomly included into the experimental group and the control group, and the experimental group was treated with Tongyuan acupuncture on the basis of routine rehabilitation treatment and drug treatment. The control group was treated with 1cm acupuncture at the same depth beside the selected points of the experimental group. Before intervention, treatment for 1 week, treatment for 2 weeks, treatment for 3 weeks, and treatment for 4 weeks (after completion), follow-up:GCS score, CRS-R scale (Modified Coma Recovery Scale) were performed 4 weeks after discharge to assess the conscious state of the patients, and EEG, brainstem evoked potential and brain fluctuation map were examined before intervention and 4 weeks after treatment. The baseline data of the experimental group and the control group showed no statistical difference through statistical analysis. Conventional rehabilitation treatment and drug treatment were adopted by the current guidelines, and the distribution of cases in the two groups was also random. |
| Study duration      | 2023.1.1-2025.12.31  |
| sample size         | 174  |

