| statistical method | Baseline data were analyzed by Chi-square test. Measurement data are expressed as mean SD. Univariate analysis of variance was used to compare the difference between groups at the same time point, the difference at different time points in the group, and the difference before and after between the two groups. $P < 0.05$ was considered statistically significant, and multiple comparisons were performed by Dunnett-t test.   |
| Expected progress  | Clinical cases will be collected from 2023.1.1 to 2024.12.30, and insufficient cases due to shedding will be added from 2025.1.1 to 2025.12.30.  |

List of abbreviations and term definitions

| abbreviation | definition                          |
|---------------------|--|
| CRS-R               | Coma Recovery Scale-Revised                |
| GCS                 | glasgow coma scale                         |
| NIHSS               | National Institutes of Health Stroke Scale |
| FOUR                | Full Outline of Unresponsiveness Scale     |

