### **13.4 Statistical software and general requirements:**

- 1)All statistical analysis was performed using SPSS25.0 statistical software.
- 2)Measurement data were described using mean, standard deviation, median, maximum and minimum values.
- 3)Counting data are described by frequency and percentage.
- 4)All data in the experiment were tested for normality.
- 5)Baseline data were analyzed using Chi-square test. Measurement data are expressed as mean SD. Univariate analysis of variance was used to compare the difference between groups at the same time point, the difference at different time points in the group, and the difference before and after between the two groups.  $P < 0.05$  was considered statistically significant, and multiple comparisons were

performed by Dunnett-t test.

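### Chi-square is the only test named for baseline data that include age and stroke duration, a finding of no baseline difference is written in advance, and the GCS comparison has no baseline covariate

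*Combined protocol and SAP*

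**What the plan says.** Section 13.3 defines the baseline set: "Baseline data included sex, age, stroke type, stroke duration, underlying medical history", followed by four comorbidities, smoking and alcohol. The next sentence gives one test for all of it: "Baseline data were tested by chi-square test". Section 13.4 repeats this ("Baseline data were analyzed using Chi-square test"), as does the statistical-method row of the Summary ("Baseline data were analyzed by Chi-square test"). No section sets age bands or duration bands, and none names a t-test or rank test for continuous baseline items.

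The study-design row of the Summary says: "The baseline data of the experimental group and the control group showed no statistical difference through statistical analysis". The same row goes on to cite guideline-based background treatment and that "the distribution of cases in the two groups was also random".

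For the outcome scores, section 13.3 says: "Univariate analysis of variance was used to compare the difference between groups at the same time point". The same analysis is to cover change within groups and the before-after difference between groups. No covariate is named for any of these. On description, section 13.4 says: "Measurement data were described using mean, standard deviation, median, maximum and minimum values".

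**The concern.** Chi-square compares counts in categories. Age (18 to 85 years) and time since stroke (up to 6 months) are measured on continuous scales, so the rule can be carried out in only two ways. Either each distinct value is treated as its own category, which leaves almost empty cells, or the values are banded with cut-points that the plan does not fix. The first makes the test nearly blind. The second loses information and leaves the bands to be chosen after the data are seen.

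The sentence in the Summary then presents non-significance as a property of the groups before any patient has been compared. Chance imbalance in a prognostic variable could be reported as absence of difference. The GCS analysis has nothing in it to correct for such an imbalance, because it is an ANOVA without covariates.

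**Working it through.** **Inputs from the documents.** Ten baseline items (sex, age, stroke type, stroke duration, four comorbidities, smoking, alcohol), a test level of 0.05, 1:1 allocation and 87 per group (sections 13.1 and 13.3).

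**The plan's own figure.** The point rests on no stated figure, but 87 per arm is used below, so it was checked first. With P = (0.794 + 0.548)/2 = 0.671, the formula in section 13.1 gives

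n = 2 × (1.96 + 1.28)² × 0.671 × 0.329 / (0.794 − 0.548)² = 76.6,

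against a stated 76. Then 76 × 1.15 = 87.4, against a stated 87. Both are reproduced closely enough for this purpose.

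**Why uncut values fail.** Ages 18 to 85 span 85 − 18 + 1 = 68 single years. With 174 patients that averages 174/68 = 2.6 patients per year of age, or about 1.3 per cell of the two-group table.

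**Simulation.** The documents give no SD or distribution, so these are assumptions: a normal variable, a true difference between arms, and the 5% level. The t-test and the banded chi-square used 20,000 runs, with two, three or four bands of about equal size. The uncut chi-square used 2,000 runs on age in whole years (mean 60, SD 12, limited to 18-85), so 0.5 SD is 6 years there.

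| Per arm | True difference | t-test | Chi-square, 2 / 3 / 4 bands | Chi-square, single years |
|---|---|---|---|---|
| 87 | 0 | 5.2% | 5.8% / 5.0% / 4.9% | about 2% |
| 87 | 0.3 SD | 50% | 37% / 33% / 30% | not run |
| 87 | 0.4 SD | 75% | 58% / 54% / 51% | not run |
| 87 | 0.5 SD | 91% | 77% / 75% / 72% | about 11% |
| 36 | 0.5 SD | 56% | 38% / 38% / 34% | not run |

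The last row is shown because section 4 gives a total of 72 patients where the Summary and section 13.1 give 174. That is a separate inconsistency.

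**The pre-written result.** Suppose randomisation is perfect and ten independent tests each hold the 5% level. Then the chance that none is significant is 0.95¹⁰ = 0.60, and the chance of at least one is 0.40. The sentence in the Summary could therefore turn out false in a properly randomised trial. If it turned out true, it still would not show that the groups were alike.

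**Why baseline GCS matters.** Section 8.1.1 divides each patient's change by the starting score and counts 15% or more as effective. A one-point gain is 1/3 = 33% from GCS 3 and 1/6 = 16.7% from GCS 6, both effective. It is 1/7 = 14.3% from GCS 7 and 1/9 = 11.1% from GCS 9, both ineffective. All four starting scores are eligible, so the starting score affects the result directly.

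**The case against.** Much can be said for the plan.

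- A reader might infer that chi-square cannot detect imbalance in age or stroke duration at all. That goes too far. On banded values it detects a 0.5 SD difference in 72-77% of simulated trials, and no section says that the test will be run on single years or days. The defect is that the plan leaves the matter open.
- The simulation shifts the underlying populations, and randomisation rules such a shift out. In SD units the standard error of a mean difference is √(2/87) = 0.15, so 0.5 SD is about 3.3 standard errors and would rarely arise by chance. The percentages therefore describe how sensitive the test is. They do not give the probability that this trial will be misled.
- A reader might infer that the claim of comparability rests on the baseline tests alone. It does not, since the Summary also cites random allocation. Section 13.4 already plans means, SDs, medians and ranges, in which a material imbalance would be visible.
- A reader might infer that baseline GCS is ignored. It is missing from the list in section 13.3, but the flow chart schedules it at baseline and the same-time-point ANOVA can be read to cover it. It also enters through the before-after difference and the improvement rate.
- The Summary uses the past tense for the design as well, so its sentence is no evidence that data had already been analysed.

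These points limit the consequence. They do not supply a suitable test for age or stroke duration, they do not justify a result stated in advance, and they do not put a baseline covariate into the GCS comparison.

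**Conclusion.** The point holds as a minor defect with a free remedy. The one test named for baseline data does not suit two of the listed variables as they stand. Under the stated assumptions (normal data, 87 per arm, a 0.5 SD difference) it flags the difference in about 11% of trials on uncut values and 72-77% on banded values, against 91% for a t-test. The order of these figures follows from the methods, but their exact size depends on the assumed SD, shape and bands.

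Changing the test would not rescue the inference, because a non-significant baseline P value does not show comparability under any test. It would also be wrong to conclude that the efficacy result is invalid. Allocation is randomised, and no exclusion, decision or analysis rule depends on a baseline P value. What is lost is a clear account of baseline balance, together with protection against chance imbalance and the precision that adjustment for baseline GCS could bring. That gain is not quantified here, because the documents give no correlation between baseline and later GCS.

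**What to change.** 1. In the Summary, delete the sentence stating that the baseline comparison found no difference.
2. In sections 13.3 and 13.4 and the Summary, replace the blanket chi-square rule with a descriptive baseline table: mean and SD, or median and range, for age, stroke duration and baseline GCS, and number and percentage for categorical items. Draw no conclusion of equality from P values.
3. If tests are kept, name a t-test or rank test for continuous items and keep chi-square for categorical ones.
4. Pre-specify the primary GCS comparison as an ANCOVA adjusted for baseline GCS, with age, stroke type and stroke duration as further covariates.

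The cost is a change of wording. Baseline GCS is already in the flow chart and the other three variables are already in the list in section 13.3. The sample size is calculated from effective rates and does not change.

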| inclusion criteria  | (1) It met the diagnostic criteria of Chinese and Western medicine for stroke, and the Glasgow coma score was between 3 and 9 points (the score was scored by the rehabilitation physician, and the patient had not used sedatives and anesthetics on the day of the score);   |

|                            |  |
|----------------------------|--|
|                            | 
(2) The patient's condition is stable, the vital signs are stable, and the onset time of consciousness disorder caused by stroke is confirmed not more than 6 months;
 
(3) Clinical and auxiliary examination confirmed that cerebral infarction or cerebral hemorrhage is the only factor leading to consciousness disorders, excluding other diseases caused by consciousness disorders;
 
(4) Aged between 18 and 85;
 
(5) Family members or authorized clients are informed and sign informed consent;
 
(6) Did not enter other clinical studies at the same time.
   |
| exclusion criteria  | 
(1) People with consciousness impairment mainly due to changes in consciousness content or special types;
 
(2) Those confirmed by examination to have carbon monoxide poisoning, brain tumor, brain trauma, brain parasitic disease, metabolic disorders;
 
(3) Patients with severe primary diseases such as liver, kidney, blood system and endocrine system and other diseases with poor prognosis and mental illness;
 
(4) Patients with severe complications such as upper gastrointestinal bleeding and secondary epilepsy;
 
(5) Those who have venous thrombosis and are currently on anticoagulant therapy.
  |
| efficiency analysis | 
Main outcome measure: GCS score
 
Secondary outcome measures: CRS-R Scale
  |
| security analysis   | 
In this experiment, acupuncture treatment was used to exclude patients with serious primary diseases of liver, kidney, blood system and endocrine system, and other diseases with poor prognosis and mental illness; If the patient's condition deteriorates during treatment and dangerous events may occur, the clinical observation of the case shall be terminated to ensure the safety of the patient.
   |

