### 1.5 Current research status of encephalofluctuograph:

Encephalofluctuograph (EFG) is a non-invasive electrophysiological technology used to detect the function of brain neurotransmitters. It collects 10 min brain waves and extracts ultra-slow waves for analysis (frequency range: 1~255 mHz). A large number of experiments have proved that dominant ultra-slow waves are related to the activity of neurotransmitters in brain. Each neurotransmitter has a one-to-one correspondence (cryptographic relationship) with ultra-slow waves of a particular frequency. Through experiments, the code of several common neurotransmitters has been deciphered, which are acetylcholine, norepinephrine, gamma-aminobutyric acid, glutamic acid, 5-hydroxytryptamine and dopamine

[19-20].At present, many domestic scholars have used brain fluctuation graph to study the changes of neurotransmitter power in different nervous system diseases, especially in the study of neurodegenerative diseases, cerebrovascular diseases, emotional disorders and other diseases, and have obtained similar results in different research groups.

He Renhong et al. [21] included 39 patients with brain injury, and then collected the neurotransmitters in the brain during EEG assessment (detected by brain fluctuation map). The detection indexes included the transmitter power, relative power and index analysis of  $\gamma$ -aminobutyric acid, 5-hydroxytryptamine, norepinephrine, dopamine and other transmitters. The results showed that the brain transmitter power of the poor outcome group was significantly lower than that of the good group. Logistic regression analysis showed that gamma-aminobutyric acid and serotonin were the factors that could significantly affect the outcome. The authors suggest that in the clinical rehabilitation of brain injury, therapeutic methods that can improve the efficacy of gamma-aminobutyric acid and serotonin transmitters should be considered.

At present, the study on the effect of acupuncture on awakening has been developed from behavior to molecular mechanism.

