## **2.purpose of research**

2.1 Main Objective: To confirm the effect of Tongyuan acupuncture on consciousness disorder after stroke;

2.2 Secondary objective: To explore the mechanism of acupuncture intervention in post-stroke consciousness disorder.

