## **3.study endpoint**

3.1 Primary endpoint: GCS score.

3.2 Secondary endpoints: CRS-R Scale (Coma Recovery Scale-Revised), EEG(electroencephalograph), BAEP (Brainstem Auditory Evoked Potential), and EFG (Encephalofluctuography).

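### The Summary and Section 3.2 give different secondary endpoints, and no variable or error control is set for EEG, BAEP and EFG, so the false-positive risk for the mechanism objective is uncontrolled

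*Combined protocol and SAP*

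**What the plan says.** **Secondary endpoints.** The efficiency-analysis row of the Summary gives "Secondary outcome measures: CRS-R Scale" and nothing more. Section 3.2 gives "3.2 Secondary endpoints: CRS-R Scale (Coma Recovery Scale-Revised), EEG(electroencephalograph), BAEP (Brainstem Auditory Evoked Potential), and EFG (Encephalofluctuography".

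**Other scales.** The flow chart and Section 7.2(2) schedule NIHSS and FOUR at baseline, at weeks 1 to 4 and at follow-up. Neither list names them as endpoints.

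**Objective served.** Section 2 states "2.2 Secondary objective: To explore the mechanism of acupuncture intervention in post-stroke consciousness disorder". EEG, BAEP and EFG are the scheduled assessments that can address it.

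**Variables.** Section 8 defines GCS and CRS-R measures only. No section names the EEG, BAEP or EFG variable to be analysed.

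**Analysis.** Section 13.3 says "The end point data was the score of the State of Consciousness scale". Sections 13.3 and 13.4 then apply univariate ANOVA to measurement data for three kinds of comparison: between arms at a given time, within an arm over time, and between arms on the before-after change. The threshold is P<0.05, which "was considered statistically significant, and multiple comparisons were performed by Dunnett-t test".

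**Timing.** Section 7.2(2) places all three tests before intervention and at treatment week 4. The flow chart, as extracted, places post-baseline BAEP and EFG under the post-discharge telephone or video contact.

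**The concern.** Two current parts of the plan disagree on which endpoints are secondary, and the tests that carry a stated objective have no defined variable. Each of EEG, BAEP and EFG can yield many numbers. If the variable is chosen after the data are seen, a reader of the report cannot tell a planned mechanism result from a selected one. NIHSS or FOUR could likewise be promoted or left out once results are known.

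The multiplicity method named does not address this. Dunnett's test compares several groups or times with one reference within a single variable. It does not adjust across variables, and with two arms at one visit it makes no adjustment. The GCS primary analysis is not affected; the interpretation of the mechanism objective is.

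**Working it through.** **Figure in the plan.** The documents state no error rate or number of tests for EEG, BAEP or EFG, so there is no figure of this kind to reproduce. The one computed design figure, about 76 per arm in Section 13.1, comes out at 2 × (1.96 + 1.28)² × 0.671 × 0.329 / 0.246² = 76.6. It does not bear on this point.

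**Which analysis applies to the three tests?**
- If the endpoint sentence in Section 13.3 governs, only a consciousness scale score is analysed, and three endpoints declared in Section 3.2 have no analysis.
- If the general rule in Section 13.4 governs, each numeric readout is measurement data. It is tested between arms at least twice: on the week-4 value and on the before-after change.

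Either reading leaves a gap. The arithmetic below belongs to the second.

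**Inputs**
- Threshold: two-sided 0.05 (Sections 13.1, 13.3 and 13.4).
- Number of readouts k: not stated, so assumed. k = 3 is one readout for each test. k = 6 is one index for each of the six transmitters that Section 1.5 lists for EFG. k = 18 is those six times three index types. The three types come from a cited study in Section 1.5: "The detection indexes included the transmitter power, relative power and index analysis".
- Correlations between readouts, and between baseline and week 4: assumed.

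**One between-arm test per readout, independent readouts, no true effect**

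Chance of at least one P<0.05 = 1 − 0.95^k
- k = 3: 1 − 0.857 = 14%
- k = 6: 1 − 0.735 = 26%
- k = 13: 1 − 0.513 = 49%
- k = 14: 1 − 0.488 = 51%
- k = 18: 1 − 0.397 = 60%

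**Equally correlated readouts, by simulation**

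| k | r = 0.3 | r = 0.5 | r = 0.7 |
|---|---|---|---|
| 3 | 14% | 13% | 11% |
| 6 | 24% | 21% | 17% |
| 18 | 51% | 40% | 28% |

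**Both planned between-arm tests per readout**

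Let the baseline-to-week-4 correlation be ρ, with equal variances. The week-4 and change statistics then correlate at √((1 − ρ)/2). At an assumed ρ = 0.6 this is √0.2 = 0.447. The bivariate normal distribution gives a 9.2% chance that at least one of the two passes 0.05 for a single readout. For 3 independent readouts: 1 − (1 − 0.092)³ = 25%. Taking ρ as 0.5 or 0.7 instead leaves this at 25% or 26%.

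The within-arm comparisons over time are not counted. They can reach significance through recovery on usual care, without any treatment effect.

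**The case against.** **A chance finding is not shown to be likely.** A reader might infer that a false mechanism result is more likely than not. The documents do not support that. With one test per readout, the risk passes 50% only from 14 independent readouts, and the plan gives no number. The count of 18 joins a general description of EFG to the index types of one 39-patient study, both in the background section. No operative section adopts either. Readouts from one recording are also unlikely to be independent, and 18 readouts give 40% and 28% at correlations of 0.5 and 0.7. This stands: 18 is a scenario only.

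**It is not settled that every readout is judged at 0.05.** That reading needs the general rule in Section 13.4 and sits against the endpoint sentence in Section 13.3. This also stands. The plan is ambiguous, and each reading leaves a different gap.

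**The aim is exploratory.** Section 2.2 is worded that way and the GCS conclusion is untouched. This lowers the consequence. It does not remove it, because Section 3.2 makes the tests formal secondary endpoints and no section withholds a significance claim.

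**The lists may have different scopes.** The Summary's list sits under efficacy, and its design row does mention the three tests. NIHSS and FOUR are grouped with consciousness assessment in Section 7.2(2), so the scale score in Section 13.3 might include them. Both are possible, and one sentence in the plan would settle each.

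**The background does not supply the variables.** Section 1.5 reports that "gamma-aminobutyric acid and serotonin were the factors that could significantly affect the outcome", but not which index was used. Section 1.1.3.2 describes BAEP latency, amplitude and loss of wave V, and a shift from alpha to slower EEG waves, without defining an analysis variable. The choice is therefore the sponsor's.

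**Conclusion.** The point holds in a limited form. The secondary endpoint lists conflict. EEG, BAEP and EFG have no named variable and no unambiguous analysis. Nothing controls error across their readouts.

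The false-positive risk for the mechanism objective is uncontrolled, and it cannot be bounded because the plan states no number of readouts. Under no true effect, a modest count of 3 independent readouts gives about 14% with one test each and about 25% with both planned between-arm tests. Larger counts give more: up to 60% for 18 independent readouts with one test each, or about 40% at a correlation of 0.5. These figures rest on assumed counts and correlations, and on the general rule in Section 13.4 applying to these tests. The matter should be corrected, but it does not threaten the primary analysis.

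**What to change.** 1. Use one secondary endpoint list in the Summary and Section 3.2, and state whether NIHSS and FOUR are secondary or exploratory.
2. Before database lock, name one key variable each for EEG, BAEP and EFG, chosen by the sponsor. If a BAEP latency is chosen, add a rule for an absent waveform. Latency is then undefined, and Section 1.1.3.2 links loss of wave V to a very poor outlook, so dropping those patients would be selective.
3. Reconcile the post-baseline time point for BAEP and EFG between the flow chart and Section 7.2(2). The table may have shifted on extraction.
4. Compare the arms once on each key variable, by ANCOVA adjusting for its own pre-treatment value, in place of the separate ANOVA comparisons in Sections 13.3 and 13.4.
5. Report the key variables and all other EEG, BAEP and EFG readouts as exploratory estimates with confidence intervals and no significance claim. If a significance claim is wanted for the key variables, apply Holm across them, which holds the family-wise error at 5% or less.

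The cost is wording, with no added patients, visits or tests. The small downside is that unselected readouts can no longer support a confirmatory mechanism claim.
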